6.2.2 Exclusion Criteria

Any patient who meets any of the following criteria will not qualify for entry into the study:

немуни	Corporate Medical Department		
Identification Number	Version Number	State	Effective date
FORM-000050125	2.0, CURRENT	Effective	08, Jan 2021

Protocol Version 1.0 of 1 23/04/2021

Study Code: MEIN/20/ZoAm-Hyp/001

- 1. Known contraindications, presence of not recommended/contraindicated concomitant therapy allergies, or significant history of hypersensitivity to zofenopril, amlodipine, other ACE-inhibitors or dihydropyridines, or any related products (including excipients of the formulations as outlined in the Investigator's Brochure [IB]), or summary of product characteristics (SmPCs) or local package inserts for AML and ZOF
- 2. Patients with serious disorders (in the opinion of the Investigator) which may limit the ability to evaluate the efficacy or safety of the tested medications, including cerebrovascular, cardiovascular, renal, respiratory, hepatic, gastrointestinal, endocrine/ or metabolic, haematological, or oncological, neurological, and psychiatric diseases. The same applies for immunocompromised and/or neutropenic patients
- 3. Patients having a history of the following within the last 6 months: myocardial infarction, unstable angina pectoris, percutaneous coronary intervention, bypass surgery, valve replacement (transcatheter aortic valve implantation, mitraclip), cerebrovascular accident (stroke, heart failure, hypertensive encephalopathy, cerebrovascular accident (stroke), or transient ischemic attack. Patients with who have undergone other surgery that in the in the opinion of the Investigator may limit the ability to evaluate the efficacy or safety of the tested medications.
- 4. Patients with secondary hypertension of any aetiology such as renal diseases, pheochromocytoma, Cushing's syndrome hyperaldosteronism, renovascular disease, thyroid disorders
- 5. Patients with severe heart failure (New York Heart Association classification III-IV), a narrowing of the aortic or bicuspid valve, an obstruction of cardiac outflow (obstructive, hypertrophic cardiomyopathy) or symptomatic coronary disease
- 6. Patients with clinical evidence of renal disease as per the Investigator's judgement (including renovascular occlusive disease, nephrectomy and/or renal transplant, bilateral renal artery stenosis or unilateral renal artery stenosis in a solitary kidney, or severe renal impairment)
- 7. Patients with history of angioneurotic oedema
- 8. Patients with clinically relevant hepatic impairment
- 9. Patients with sick sinus syndrome, including sino-atrial block
- 10. Patients with second- or third-degree heart block (without a pacemaker)
- 11. Participation in any other interventional drug trial or exposure to other investigational agents within 30 days before Screening (Visit 1)
- 12. Inability to cooperate or any condition that, in the opinion of the Investigator, could increase the patient's risk of participating in the study or confound the outcome of the study

MENARINI	Corporate Medical Department		
Identification Number	Version Number	State	Effective date
FORM-000050125	2.0, CURRENT	Effective	08, Jan 2021

- 13. Patients with conditions that, in the opinion of the Investigator, would prevent a careful adherence to the protocol
- 14. Patients with severe hypotension
- 15. Patients who suffer from shock (including cardiogenic shock)
- 16. Patients treated with Amlodipine 10 mg and Zofenopril (other than 30 mg)

6.2.3 Screening Failures

All patients who have signed an informed consent form but do not enter into the Run-in period (failure to meet at least one of the inclusion criteria and/or met at least 1 of the exclusion criteria) will be classified as a screening failure. Screening failures need to have the screening completion eCRF for run-in period, demographics, inclusion / exclusion criteria and any SAE collected. There will be no re-screening allowed for screening failure patients.

7 STUDY TREATMENT

7.1 Study Treatment Formulation, Appearance, Packaging, and Labeling

Zofenopril calcium will be provided as 30 mg film coated tablets

Amlodipine (as besylate) will be provided as 5 mg and 10 mg tablets

The treatments administered during the run-in period of the study are AML 5 mg tablets or ZOF 30 mg film-coated tablets. The patients who are eligible (uncontrolled hypertension with sitting BP of SBP/DBP >130/80 mmHg, who tolerated the treatment and whose adherence to the therapies ranges from 80% to 120%) for the assessment period will be given a combination of AML 5 mg and ZOF 30 mg or AML 10 mg and ZOF 30 mg. Details on the study design is provided in Section 5.

MENAFINI	Corporate Medical Department		
Identification Number	Version Number	State	Effective date
FORM-000050125	2.0, CURRENT	Effective	08, Jan 2021

Sponsor: Menarini International Operations Luxembourg SA Protocol Version 1.0 of 1 23/04/2021

Study Code: MEIN/20/ZoAm-Hyp/001

Study Treatment Name:	Amlodipine	Zofenopril calcium
	Marketing Authorisation Holder:	Marketing Authorisation Holder:
	EG S.p.A.	Laboratori Guidotti S.p.A Via
	[name]	[name]
	[name]	Concessionario per la vendita: A.
	Italy	Menarini Industrie Farmaceutiche
		Riunite s.r.l., [name]
		Firenze, Italy
Dosage Formulation:	Tablets	Film-coated tablets
Unit Dose Strength(s)/Dosage	5 mg once daily	30 mg once daily
Level(s):	10 mg once daily	
Route of Administration:	Oral	Oral
Dosing Instructions*:	1 tablet of study medication to be	1 tablet of study medication to be
	administered with water, once daily	administered with water, once daily and
	and according to instructions provided	according to instructions provided by
	by Principal Investigator	Principal Investigator
Packaging and Labelling:	Study medication will be provided in	Study medication will be provided in its
	its original marketed PVC//Aluminium	original marketed a
	blisters	PVDC/PVC//Aluminium blisters
Storage Conditions:	All study treatment must be stored in	All study treatment must be stored in its
	its original packaging and kept in a	original packaging and kept in a secure
	secure area (in a dry place and	area (in a dry place and protected from
	protected from light and in accordance	light and in accordance with the label's
	with the label's instructions) with	instructions) with access limited to the
	access limited to the Investigator and	Investigator and authorized site staff. No
	authorized site staff. No other special	other special storage conditions are
	storage conditions are needed.	needed.

Study treatment dosage form, strength, formulation:

Amlodipine 5 mg: AML 5 mg is white, round, tablet

Amlodipine 10 mg: AML 10 mg is white, round, tablet with one break on one side

МЕМАЯМ	Corporate Medical Department		
Identification Number	Version Number	State	Effective date
FORM-000050125	2.0, CURRENT	Effective	08, Jan 2021

Zofenopril calcium 30 mg: ZOF 30 mg is white, oblong film-coated tablet with break marks on both sides.

Study treatment manufacturing

The AML 5/10 tablets and ZOF 30 mg film-coated tablets will be sourced as authorized EU marketed products from a commercial supplier in the European market.

Marketing Authorization Holders (MAH) are reported in relative SmPC^{7,8}.

Study treatment packaging and labelling

The study treatment packaging and labelling operations are performed by A. Menarini Manufacturing Logistics and Services S.R.L. (Menarini Group), [name].

The study treatment packaging and labelling operations will be performed in compliance with all applicable regulatory requirements and Good Manufacturing Practice guidelines, as well as any additional national requirement and Standard Operative Procedures (SOPs).

The label wording will be in the local language for each country and will report the contents of

The label wording will be in the local language for each country and will report the contents of the boxes and the instructions on how to administer and store the study medication.

Study treatment packaging description

Both ZOF 30 mg and AML 5/10 mg will be provided in dedicated treatment Patient Kits to be dispensed at Visit 1 (Run In) and at Visit 2 and Visit 3 (Assessment).

Visit 1 (Screening- start Run In)

- ZOF 30 mg: each trial participant is provided with one labelled Patient Kit (blue label) containing 42 film-coated tablets (3 blisters of 14 tablets each) of zofenopril calcium 30 mg.
- AML 5 mg: each trial participant is provided with one labelled Patient Kit (yellow label) containing 42 tablets (3 blisters of 14 tablets each) of amlodipine 5 mg.

Trial participant must be instructed by Investigator to take one tablet of ZOF 30 mg or AML 5 mg, according to Study Protocol.

МЕМАЯМ	Corporate Medical Department		
Identification Number	Version Number	State	Effective date
FORM-000050125	2.0, CURRENT	Effective	08, Jan 2021

Visit 2 (start of Assessment)

Participants with uncontrolled BP (>130/80 mmHg) will be provided with ZOF 30 mg and AML 5 mg while participants with controlled BP (≤130/80 mmHg) will be withdrawn from the study

Each trial participant is provided with one treatment Patient Kit made up by

- ZOF 30 mg: one labelled box (white label) containing 42 film-coated tablets (3 blisters with 14 film coated tablets each) of zofenopril calcium 30 mg
- AML 5 mg: one labelled box (white label) containing 42 tablets (3 blisters with 14 tablets each) of amlodipine 5 mg.

The two white labelled boxes are then sealed together into a transparent plastic film to realize the treatment Patient Kit.

Trial participant must be carefully instructed by Investigator to take simultaneously (at the same time): ZOF 30 mg (zofenopril calcium 30 mg) as one oblong film-coated tablet and AML 5 mg (amlodipine 5 mg) as one round tablet, according to Study Protocol.

Visit 3 (Assessment)

Participants with controlled BP (≤130/80 mmHg) are provided with one treatment kit made up by:

- ZOF 30 mg: one labelled box (white label) containing 42 film-coated tablets (3 blisters with 14 film coated tablets each) of zofenopril calcium 30 mg
- AML 5 mg: one labelled box (white label) containing 42 tablets (3 blisters with 14 tablets each) of amlodipine 5 mg.

The two white labelled boxes are then sealed together into a transparent plastic film to realize the treatment kit.

Trial participant must be carefully instructed by Investigator to take simultaneously (at the same time): ZOF 30 mg (zofenopril calcium 30 mg) as one oblong film-coated tablet and AML 5 mg (amlodipine 5 mg) as one round tablet, according to Study Protocol.

Participants with SBP/DBP values classified as Grade 3 hypertension will be withdrawn from the study

Participants with uncontrolled BP (>130/80 mmHg) are provided with one treatment Patient Kit made up by:

иемани	Согр	porate Medical Departm	ent
Identification Number	Version Number	State	Effective date
FORM-000050125	2.0, CURRENT	Effective	08, Jan 2021

- o ZOF 30 mg: one labelled box (green label) containing 42 film-coated tablets (3 blisters with 14 film coated tablets each) of zofenopril calcium 30 mg
- o AML 10 mg: one labelled box (green label) containing 42 tablets (3 blisters with 14 tablets each) of amlodipine 10 mg.

The two green labelled boxes are then sealed together into a transparent plastic film to identify the treatment Patient Kit.

Trial participant must be carefully instructed by Investigator to take simultaneously (at the same time): ZOF 30 mg (zofenopril calcium 30 mg) as one oblong film-coated tablet and AML 10 mg (amlodipine 10 mg) as one round tablet (with one break on one side), according to Study Protocol

7.2 Study Treatment Distribution and Return / Destruction

All the study drugs must be retained at the investigational site for accountability, destruction and return of study supplies.

The investigator or designee will acknowledge receipt of the investigational product, documenting shipment content and condition.

Accurate records of all investigational product dispensed, used, returned, and/or destroyed must be maintained.

The investigator is responsible for ensuring the retrieval of all study supplies from patients.

At the conclusion of the study, any unused investigational product will either be destroyed at the investigator site or be returned to the Sponsor or its designee for destruction and destruction will be documented appropriately.

If no supplies remain, this fact will be documented appropriately

Destruction of returned investigational products must carried out after written authorization of the Sponsor

7.3 Product Storage and Stability

No special storage conditions are required. However, the verification of the storage conditions along with the relevant records will be monitored at the trial site.

MENARINI	Corporate Medical Department		ent
Identification Number	Version Number	State	Effective date
FORM-000050125	2.0, CURRENT	Effective	08, Jan 2021

All study treatment must be stored in its original packaging and kept in a secure area (in a dry place and protected from light and in accordance with the label's instructions) with access limited to the Investigator and authorized site staff.

7.4 Study Product Compliance

The investigator must promote compliance by instructing the patient to the study treatment exactly as prescribed and by stating the compliance is necessary for the patient's safety and the validity of the study. The investigator has to instruct patients to return the study treatment (if any or empty boxes for accountability) at each visit.

Investigator should instruct the patient to take the study drug at the same time every day, in the morning. On the days of the patient's visits, the investigator should instruct the patient to not take the study drug at home.

In case a patient forgets to take a dose, he/she can by take the study drug the same day. Patients should not take the study drug after 16.00 (4 pm) on the visit days. The investigator should instruct the patient to not take the dose at home.

The compliance to the treatment (percentage of actual doses taken versus doses to be taken) will be assessed by the investigator and/or study personnel at Visit 2 (Week 0), at Visit 3 (Week 4) and at Visit 4 (Week 8). This information should be captured in the source document and in the eCRFs at each visit.

Adherence to treatment will be measured through treatment compliance which is $100 \times$ (actual doses taken/planned dose).

A patient who has taken at least 80% and no more than 120% of the required study medication intake since the last visit will be considered as compliant.

7.5 Concomitant Therapy(ies)

The investigator must instruct the patient to notify the study site about any new medication he/she takes after being enrolled into the study. All medication, procedures and significant non-drug therapies administered after the patient was enrolled at the study must be recorded in the

MENARINI	Corporate Medical Department		
Identification Number	Version Number	State	Effective date
FORM-000050125	2.0, CURRENT	Effective	08, Jan 2021

Sponsor: Menarini International Operations Luxembourg SA Study Code: MEIN/20/ZoAm-Hyp/001	Protocol Version 1.0 of 1	23/04/2021
Simily Could 1/22/1 (20/20/20/20/20/20/20/20/20/20/20/20/20/2		

appropriate eCRF. Each concomitant drug must be individually assessed against all exclusion criteria/prohibited medication. If the patient is already enrolled, please contact BIORASI to determine if the patient should continue participation in the study.

7.6 Not permitted medications

Blood pressure modifying drugs, even though used for other indications like alpha receptor blockers and agonists, beta receptor blockers and agonists, calcium antagonists, angiotensin converting enzyme (ACE) inhibitors, diuretics, centrally acting antihypertensives (e.g. clonidine, methyldopa, guanfacine), reserpine, moxonidine, chronic nitrate treatment (e.g. isosorbide dinitrate or isosorbide mononitrate), potassium sparing diuretics, potassium supplements, potassium-containing salt substitutes or other agents that increase serum potassium, PDE - inhibitors and angiotensin II antagonists will be prohibited during the study.

The Investigator has to instruct patients to refer to the study doctor before they administer any medicinal substances or products listed in section 4.5 of the Zofenopril and Amlodipine SmPC^{7.8}.

7.7 Rescue Medicine

Not Applicable.

8 STUDY ASSESSMENT AND PROCEDURES

The following study assessment and procedures will proceed according to the Study Flow Chart in Section 2.3.

Informed Consent

A signed and dated, study-specific, Independent Ethics Committee (IEC) approved consent form must be obtained from each patient at the Screening Visit and prior to performing any study related procedures. No study related procedures or activities may be performed until each patient is fully informed and the consent form is duly read, understood, signed and dated. All patients will be given a copy of the signed and dated consent form. The Investigator must store

МЕМАЯМ	Согр	porate Medical Departmo	ent
Identification Number	Version Number	State	Effective date
FORM-000050125	2.0, CURRENT	Effective	08, Jan 2021

the originally signed ICF in the Investigator's File, and the patient will be provided with a copy of it. For more details, please refer to Section 6.

Inclusion/Exclusion Criteria

All patients who sign the ICF will be evaluated for inclusion and exclusion criteria to determine patient eligibility as described in Section 6.1. If the patient is determined to be ineligible prior to enrolment, the reason(s) for ineligibility must be documented by the Investigator. Verification of all inclusion and exclusion criteria, including all baseline assessments, will take place at the Screening Visit.

Medical History

A complete medical history for each patient will be recorded at the Screening Visit. A complete review of all current diseases, history of hypertension, and their respective durations and treatments will be conducted, and the relevant documentations will be filed in the Source Documentation.

Prior medication

At the Screening Visit, all medications taken within the 30 days prior to the start of the study will be recorded as Prior Medication with the corresponding indication, start and stop dates. Prior medications may include prescription, over-the counter (OTC) and all dietary supplements. A particular focus will be on prior medication to treat hypertension including zofenopril or amlodipine status and dosage.

Demography

After the informed consent has been signed and the patient's eligibility to participate in the study has been determined at the Screening Visit, basic demographic information, including age, gender, race, height, and weight. The BMI (kg/m²) will be calculated will be recorded. Smoking status will be documented in the source documents and Ecrf. For female patients, the menopausal status would also be documented.

IWRS registration:

МЕМАЯМ	Corporate Medical Department		
Identification Number	Version Number	State	Effective date
FORM-000050125	2.0, CURRENT	Effective	08, Jan 2021

At Visit 1 all screened patients will be registered via Interactive (IWRS) to one of the allocated treatments: zofenopril 30 mg and amlodipine 5 mg. The investigator or his/her delegate will contact the IWRS after confirming that the patient fulfils all the inclusion /exclusion criteria. The percentage of enrolled patients coming from each monotherapy treatment, Zofenopril 30 mg / Amlodipine 5 mg will be capped at 50% at Visit 2.

IWRS must be updated at each visit, registering the status of the patient (failure, ongoing and which therapy the patient's is administering)

Concurrent diseases and medical conditions

At each of the study visits (1, 2, 3, and 4) current diseases and medical conditions will be recorded including their date/time of diagnosis, duration, and treatment. Adverse event will be conditions arising after the start of the study, which should be recorded as adverse events as described in Section 9.1.

Monotherapy of zofenopril 30 mg or amlodipine 5 mg dispensing

- At the Screening Visit (Visit 1):
 - o Patients who are currently being treated with zofenopril (ZOF) 30 mg or amlodipine (AML) 5 mg will continue the same therapy for 4 weeks.
 - o Patients on any other ACE-i will be assigned to monotherapy with ZOF 30 mg for 4 weeks.
 - o Patients on other CCBs (the allowed CCBs are: felodipine, isradipine, lacidipine, lercanidipine, nicardipine, nifedipine, and nisoldipine) will be assigned to monotherapy with AML 5 mg for 4 weeks.

The study drugs will be dispensed such that patients have sufficient supply to last until the next visit (Visit 2). All patients will be counselled to keep the packaging and any remaining drug to be surrendered during Visit 2.

Extemporaneous combination of ZOF/AML 30/5 mg dispensing

At Visit 2 (after the run-in period (4 weeks \pm 2 days) of monotherapy) if BP remains uncontrolled (sitting SBP/DBP >130/80 mmHg), treatment is well tolerated and adherence to

MENARINI	Corporate Medical Department		ent
Identification Number	Version Number	State	Effective date
FORM-000050125	2.0, CURRENT	Effective	08, Jan 2021

the treatments ranges from 80% to 120%, patients will enter the assessment period, where they will be assigned to the extemporaneous combination of ZOF 30 mg and AML 5 mg. The study drugs will be dispensed such that patients have sufficient supply to last until the next visit (Visit 3). All patients will be counselled to keep the packaging and remaining drug to be collected during Visit 3.

At Visit 2 patients with SBP/DBP values classified as Grade 3 hypertension (SBP \geq 180 or DBP \geq 110 mmHg) will be withdrawn from the study.

At Visit 3, if BP is controlled (\leq 130/80 mmHg), patients will continue the same extemporaneous combination ZOF/AML 30/5 mg for additional 4 weeks \pm 2 days (Visit 4).

Extemporaneous combination of ZOF/AML 30/10 mg dispensing

At Visit 3, if BP is controlled, patients will continue the same extemporaneous combination for additional 4 weeks \pm 2 days (Visit 4). Uncontrolled patients (sitting SBP/DBP >130/80 mmHg), will be up titrated from AML 5 mg to AML 10 mg for further 4 weeks \pm 2 days (Visit 4).

At Visit 3 patients with SBP/DBP values classified as Grade 3 (SBP \geq 180 or DBP \geq 110 mmHg) hypertension will be withdrawn from the study

Study drug return/accounting (Compliance assessment)

The study drugs will be dispensed on site such that patients have sufficient supply to last until the next visit. All patients will be counselled to keep the packaging and remaining drug to be returned to the site staff at the subsequent visit. Site staff will collect the unused drug and packaging and provide an assessment of compliance at Visits 2, 3, and 4.

Concomitant medications

Any medication that the patient was receiving at the time of enrolment, and the other regular or occasional use of any concomitant medication during the study will be recorded in the source documents and in the eCRF. The concomitant medications will be recorded at the Screening Visit and each subsequent visit during the study.

MENARINI	Corporate Medical Department		ent
Identification Number	Version Number	State	Effective date
FORM-000050125	2.0, CURRENT	Effective	08, Jan 2021

Sponsor: Menarini International Operations Luxembourg SA

Protocol Version 1.0 of 1 23/04/2021

Study Code: MEIN/20/ZoAm-Hyp/001

8.1 Assessment of Efficacy

The primary objective of this study is to assess the anti-hypertensive efficacy of the extemporaneous combination of ZOF 30 mg in combination with AML 5 mg or AML 10 mg in lowering the sitting diastolic BP between Visit 2 (Week 0) and Visit 4 (Week 8) in patients with uncontrolled BP previously treated with Zofenopril or Amlodipine (5 mg) monotherapies for at least 4 weeks. The primary efficacy endpoint is change in mean sitting DBP between Visit 2 (Week 0) and Visit 4 (Week 8). To achieve this objective, the efficacy parameter BP will be measured at all visits as described below.

Blood Pressure (BP)

BP will be measured in both arms at the screening visit (Visit 1) to detect possible between-arm differences. The arm with the higher value of mean DBP will be identified as the reference arm and will be used at all subsequent visits for BP monitoring. Blood pressure measurements should be performed as nearly as possible at the same time of the day (7:00 - 12:00 a.m.), on the same arm, and using the same calibrated equipment at each visit.

All BP measurements will be performed after at least 10 minutes rest in sitting position in triplicate (spaced by at least 1 minute) and once standing using an automatic device provided by MENARINI. The mean of the three recordings in sitting position will be used as the BP value for that visit and recorded in the source document and in the eCRF. All BP measurements during the treatment phase will be performed as through readings (i.e. 24 + 2 h after the last drug intake). Thus, the study drug should be taken at morning time Post-BP measurement. For this purpose, patients will be instructed to take study treatment at the same time each day except on the days of study visits when study treatment will be taken after all visit evaluations have been performed.

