### 3.1.3 Exploratory Objectives

- **Objective 3.1**: To assess change in mean sitting SBP and DBP between Visit 1 (Week -4) and Visit 2 (Week 0), Visit 3 (Week 4) and Visit 4 (Week 8).
- **Objective 3.2**: To assess the antihypertensive efficacy at different time points in patients who (1) received ZOF or AML monotherapies before the run-in period, (2) received any other ACE-i or CCB monotherapies before the run-in period.

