### 3.2.3 Exploratory Endpoints

- Endpoint 3.1: Change in mean sitting SBP and DBP between Visit 1 (week -4) and Visit 2 (Week 0), visit 3 (Week 4) and Visit 4 (Week 8):
  - In the group of patients who were on ZOF 30 mg and AML 5 mg at Visit 1 (Week -4) and continued the same therapies.

- In the group of patients who switched to ZOF 30 mg or AML 5 mg from any other ACE-i or CCBs at Visit 1 (Week -4).
- Endpoint 3.2: Change in mean sitting SBP and DBP for uncontrolled patients at Visit 3 (Week 4), between Visit 2 (Week 0) and Visit 3 (Week 4).
  - In the group of patients who were on ZOF 30 mg and AML 5 mg at Visit 1 (Week -4) and continued the same therapies.
  - In the group of patients who switched to ZOF 30 mg or AML 5 mg from any other ACE-i or CCBs at Visit 1 (Week -4).
- Endpoint 3.3:
  - Monotherapy: number and proportion of patients achieving the BP goal (sitting BP≤130/80 mmHg) at Visit 2 (Week 0):
    - In the group of patients who were on ZOF 30 mg and AML 5 mg at Visit 1 (Week -4) and continued the same therapies.
    - In the group of patients who switched to ZOF 30 mg or AML 5 mg from any other ACE-i or CCBs at Visit 1 (Week -4).
  - Combination therapy: number and proportion of patients achieving the BP goal (sitting BP≤130/80 mmHg) at Visit 3 (Week 4):
    - In the group of patients who were on ZOF 30 mg and AML 5 mg at Visit 1 (Week -4) and continued the same therapies.
    - In the group of patients who switched to ZOF 30 mg or AML 5 mg from any other ACE-i or CCBs at Visit 1 (Week -4).

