### 7.4.1 Mean Change (Endpoints 3.1 and 3.2)

**Endpoint 3.1**: Change in mean sitting SBP and DBP between Visit 1 (Week -4) and Visit 2 (Week 0), Visit 3 (Week 4) and Visit 4 (Week 8).

**Endpoint 3.2**: Change in mean sitting SBP and DBP for uncontrolled patients at Visit 3 (Week 4), between Visit 2 (Week 0) and Visit 3 (Week 4).

Endpoints 3.1 and 3.2 will be analyzed using mixed models for repeated measured (MMRM) to assess the mean change in SBP and DBP. The models will be built as follows:

- Endpoint 3.1
  - *Response* = change from screening BP
  - *Covariates* = treatment subgroup, study visit, treatment subgroup-by-visit interaction, screening BP values
  - *Random effect* = patient
  - Covariance matrix = unstructured
    - In the event of lack of model convergence, other covariance structures may be used.
    - If all MMRM fail to converge, this endpoint will be analyzed as described in section 7.4.1.1 below.
- Endpoint 3.2
  - *Response* = change from baseline BP

- *Covariates* = treatment subgroup, study visit, treatment subgroup-by-visit interaction, baseline BP values
- *Random effect* = patient
- *Covariance matrix* = unstructured
  - In the event of lack of model convergence, other covariance structures may be used.
  - If all MMRM fail to converge, this endpoint will be analyzed as described in section 7.4.1.1 below.

Least-squares (LS) means, standard error (SE), and 95% CIs for mean change from screening/baseline for BP will be presented by visit and treatment subgroup. The LS-means difference, SE, 95% CI, and two-sided p-value for the difference between treatment subgroups in mean change from screening/baseline for sitting SBP and DBP will be presented where a p-value of  $\leq$  0.05 indicates a significant difference between groups.

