### 8.4 Vital Signs

Vital signs are collected at each study visit and include the following parameters: Systolic Blood Pressure (SBP), Diastolic Blood Pressure (DBP), Heart Rate (HR), and Temperature (temp). Vital sign parameters will be analyzed for the SAF population as follows:

Monotherapy analysis: observed values and change from Screening (Visit 1) to Baseline (Visit 2) will be summarized for each monotherapy group (ZOF 30 mg and AML 5 mg) and for All Patients.

Combined therapy analysis: observed values and change from Baseline (Visit 2) to scheduled postbaseline visits (Visits 3 and 4) will be summarized for each combined therapy group (ZOF/AML 30/5 mg or ZOF/AML 30/10 mg) and for All Patients.

All vital sign parameters will also be presented in a by-patient data listing for the SAF population.

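### If the higher arm's Visit 1 reading is kept as the Visit 1 value, as Protocol 8.1 most naturally reads, change from Visit 1 includes a DBP fall that no drug caused (about 0.1 to 2 mmHg under assumed inputs)

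*Protocol*

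**What the plan says.** Protocol 8.1 (Blood Pressure): "BP will be measured in both arms at the screening visit (Visit 1) to detect possible between-arm differences". It continues: "The arm with the higher value of mean DBP will be identified as the reference arm and will be used at all subsequent visits". Readings are in triplicate, and "The mean of the three recordings in sitting position will be used as the BP value for that visit". The section also asks for the same arm and the same calibrated equipment at every visit. It does not say which arm's mean is recorded for Visit 1, nor does it describe a repeat set once the arm is chosen. Protocol 5.1 lists a single BP measurement at Visit 1, and the run-in starts the same day.

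The Visit 1 value is used in these places:

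- **Inclusion criterion 1** applies the SBP and DBP limits to the screening value.
- **Endpoint 3.1** (SAP 3.2.3) is "Change in mean sitting SBP and DBP between Visit 1 (week -4) and Visit 2", then Visits 3 and 4. SAP 7.4.1 sets the model response as "change from screening BP", with screening BP as covariate, and reports LS means with 95% CIs by visit and subgroup.
- **Monotherapy vital signs** (SAP 8.4, Table 14.3.6.1): "observed values and change from Screening (Visit 1) to Baseline (Visit 2) will be summarized for each monotherapy group".

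The Table 14.2.4.1 shell for Endpoint 3.1 differs from SAP 7.4.1. Only its Visit 2 row is change from Visit 1; the Visit 3 and Visit 4 rows are change from Visit 2, although the table title refers to Visit 1 throughout.

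**The concern.** When the larger of two noisy measurements is selected and kept, its error is positive on average. At Visits 2 to 4 the chosen arm is measured without any selection, so its error averages zero. If the selected reading is the Visit 1 value, the mean change from Visit 1 is negative with no change in the patients.

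The study has no randomised control, so nothing absorbs this in a within-group change. The screening-BP covariate does not remove it either, because LS means are evaluated at the average screening value, which carries the same shift. Part of what is presented as the BP fall during monotherapy would be an artefact. That includes the patients who continued their previous drug and started nothing new at Visit 1. The inflated value would also help some patients reach the entry limit.

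SBP is taken from the same arm. It would move in the same direction to the extent that SBP and DBP errors are correlated; I have not put a size on that.

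**Working it through.** **Inputs.** From the documents: the selection rule, the triplicate mean as visit value, and both arms at Visit 1 only (Protocol 8.1). The plan states no figure for this effect, so there is none to reproduce. The only DBP SD given is 10 mmHg, for the change from Visit 2 to Visit 4 (Protocol 12.2); it is neither a within-visit nor a between-arm SD. Two quantities must be assumed:

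- s = error SD of one arm's triplicate mean, specific to that arm and occasion
- D = SD of the lasting left-right difference, taken as centred on zero

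**Formula.** The observed left-minus-right difference has SD √(2s² + D²). The covariance of the error difference with it is 2s². The expected error in the higher arm's mean is half the expected error difference in the direction of selection:

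½ · [2s² / √(2s² + D²)] · √(2/π) = s² / √(π(s² + D²/2))

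With D = 0 this is s/√π = 0.564s. Variation between visits that both arms share drops out.

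**Numbers.** Examples: s = 2, D = 4 gives 4/√(π·12) = 4/6.14 = 0.65. s = 1, D = 6 gives 1/√(π·19) = 1/7.73 = 0.13.

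Drug-free DBP fall from Visit 1 to Visit 2 (mmHg):

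| s | D = 0 | D = 4 | D = 6 |
|---|---|---|---|
| 1 | 0.56 | 0.19 | 0.13 |
| 1.5 | 0.85 | 0.40 | 0.28 |
| 2 | 1.13 | 0.65 | 0.48 |
| 3 | 1.69 | 1.23 | 0.98 |
| 3.5 | 1.97 | 1.54 | 1.26 |

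The 10 mmHg SD gives only a loose ceiling. If all of it were arm-specific error, s = 10/√2 = 7.07 and the fall would be 7.07/√π = 4.0 mmHg.

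**Check by simulation.** I used 1,000,000 patients per setting, with no drug effect and no entry limits. The SD of the Visit 2 to Visit 4 change came out at 9.4 to 10.4, close to the plan's 10. The simulated falls agree with the formula: 1.13 at s = 2, D = 0; 0.65 at s = 2, D = 4; 1.23 at s = 3, D = 4. When the chosen arm is measured again at Visit 1 and only the new set is used, the fall is zero to within 0.03 mmHg. The Visit 2 to Visit 4 change is zero to within 0.01 mmHg.

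**Where it reaches.**

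- Primary endpoint and Endpoint 2.1 (Visit 2 to Visit 4) and Endpoint 2.2 (Visit 3 to Visit 4): not affected, because Visit 1 is not used.
- Endpoint 3.1, Visit 2 row, LS mean within each subgroup: affected.
- Endpoint 3.1, Visits 3 and 4: affected under SAP 7.4.1, not under the Table 14.2.4.1 shell.
- Endpoint 3.1, continued minus switched: the same rule applies in both subgroups, so the bias cancels unless s or D differs between them.
- Table 14.3.6.1, change by monotherapy group: affected.

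**The case against.** **The premise is inferred.** Protocol 8.1 does not say that the selected reading is the Visit 1 value, and Listing 16.2.9 has a left/right column, so data from both arms may be held. This stands, and the point is conditional on it. The same-arm requirement and the absence of any repeat set make the inference the natural one.

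**The size cannot be derived.** This stands too. A reader might infer that the artefact is 1 to 2 mmHg. The documents do not support that: it needs s between 1.77 and 3.54 if D = 0, or between 2.61 and 4.26 if D = 4, and neither input is given. Smaller errors or larger arm differences give a few tenths of a mmHg.

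**No false-positive claim follows.** A reader might go on to infer that the artefact is likely to produce a significant fall on monotherapy. The SAP plans no test of within-group change from Visit 1 against zero. Its only p-value for Endpoint 3.1 is the "two-sided p-value for the difference between treatment subgroups in mean change from screening/baseline for sitting SBP and DBP", where the bias largely cancels. Table 14.3.6.1 is descriptive, without CI or p-value. Any probability that a subgroup CI excludes zero would need subgroup sizes the documents do not give (the 1:1 target is between drug classes, not between continued and switched patients). It would also need an SD for Visit 1 to Visit 2, whereas the stated 10 mmHg is for another interval. The 2 mmHg null used for sizing belongs to the primary endpoint and is not a yardstick here.

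**The outputs are exploratory or descriptive, and already confounded.** Patients enter because their BP is high at Visit 1, so some fall is expected from the entry limits alone. This stands: the fix would not turn the Visit 1 change into a clean drug effect. It would remove one avoidable component whose direction is known.

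**Conclusion.** The point holds in limited form. If the higher arm's Visit 1 mean is recorded as the Visit 1 BP, within-group change from Visit 1 to Visit 2 overstates the DBP fall by s²/√(π(s² + D²/2)). That is about 0.1 to 2 mmHg for s = 1 to 3.5 and D = 0 to 6 mmHg. Both ranges are assumptions, as are independent errors in the two arms and a left-right difference centred on zero. The direction does not depend on the chosen values, provided s is above zero.

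The consequences are confined to the Endpoint 3.1 subgroup LS means, Table 14.3.6.1 and the value that decides inclusion criterion 1. Whether Visits 3 and 4 are affected depends on which of SAP 7.4.1 and the Table 14.2.4.1 shell is followed. The trial's primary conclusion is not at risk. This is a cheap improvement to the measurement procedure and a clarification the protocol needs in any case.

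**What to change.** 1. **Protocol 8.1.** Choose the reference arm from the both-arm means, as now. Then take a new sitting triplicate on that arm at Visit 1, and state that only this triplicate is the Visit 1 BP for inclusion criterion 1, Endpoint 3.1 and Table 14.3.6.1. Choosing the arm from one quick reading per arm would save time, but it makes the choice noisier, and the chosen arm is then used at every later visit, including those of the primary endpoint.
2. **SAP 7.4.1 and the Table 14.2.4.1 shell.** Reconcile the reference visit for the Visit 3 and Visit 4 rows.
3. **Patients already screened without a second set.** Footnote the Visit 1 changes as including this selection effect.

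**Cost.** Three more cuff readings, a few minutes, at Visit 1, with no new equipment. Slightly fewer patients will reach the entry limit through a chance high reading; the documents give no basis for saying how many. The new set removes the whole effect only if its error is independent of the first set, so a deviation in one arm that persists through the visit would remain. The fall due to the BP entry limits is separate and also remains.
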